7.2.1.2 Overall Response Rate

Tumor response will be assessed by the investigator based on the revised RECIST guidelines (Version 1.1) at each radiographic assessment. Radiological exams are required every 8 weeks (± 7 days) starting from date of randomization without delays for toxicity until protocol-defined disease progression is noted. Results based upon scans performed after start of new anti-cancer therapy will be excluded when calculating the best overall response. Objective response rate will be defined as the proportion of subjects with a complete response (CR) or a partial response (PR) per RECIST based upon the best response as assessed by the investigator; confirmation of response is not required. Clinical benefit rate (CBR) will be defined as the proportion of subjects with a complete response (CR), a partial response (PR), or stable disease (SD) per RECIST based upon the best response as assessed by the investigator. The analysis of ORR and CBR will be performed using Fisher's exact test to compare the relative rate of subjects with an objective response in the treatment groups without stratification. Clopper-Pearson exact 2-sided 95% confidence limits will be calculated for the proportion of subjects with ORR in each arm.

Since the presence of measurable disease is an inclusion criterion, the denominator for the rate will be the number of subjects in the FAS. In addition to representing ORR and CBR, the best overall response (BOR) using response categories CR, PR, SD, progressive disease (PD), and not evaluable (NE) will be tabulated. The proportion of subjects in each response category will be calculated for the study cohorts and the integrated treatment groups.

Subjects who do not have any post-baseline tumor assessment will be counted under the category Not Evaluable (NE).

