10.3.3.7 Day 28 (Cycle 2 and then Every Other Cycle)

- CT or MRI scans for tumor measurement (as assessed by RECIST v1.1)

During treatment, scans will be conducted from Cycle 2 (Day 28) and then be repeated every other cycle, ie, Cycle 4 (Day 28), Cycle 6 (Day 28), etc. Tumor measurements by CT or MRI scans will be conducted every 8 weeks in subjects receiving SoC in 3-weekly treatment cycles (the study day of this assessment will vary from cycle to cycle; see [Table 5](#)).

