11.2 Antitumor Effect – Solid Tumors

In this study, tumor response will be evaluated using RECIST v1.1. Tumor measurements are to be obtained for objective tumor assessment at baseline and on Day 28 of every second treatment cycle (ie, every 8 weeks), as detailed in Section 10.3, Table 3 and Table 4. Tumor measurements by CT or MRI scans will be conducted every 8 weeks in subjects receiving SoC in 3-weekly treatment cycles (the study day of this assessment will vary from cycle to cycle; see Table 5). A tumor measurement should be obtained at the End of Study/Early Termination visit, if no disease progression was confirmed previously and this visit occurs > 4 weeks after the last scan; no additional scans will be required if disease progression is confirmed at this visit. A tumor measurement should be obtained at the Safety Follow-up visit, if no disease progression was confirmed previously and this visit occurs > 4 weeks after the last scan.

For an individual subject, the method (CT and/or MRI scan) used to measure tumor burden at baseline should be used for each subsequent tumor assessment. Baseline tumor measurements and identification of target lesions may be based on imaging obtained within 28 days prior to first imalumab administration (C1D1). Scheduled tumor response assessments must be interpreted prior to the start of the next treatment cycle. A subject's best overall response will be determined at the End of Study/Early Termination Visit.

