^e Vital signs, including body temperature, heart rate, blood pressure, and respiratory rate, are to be measured after a 5-minute rest. Sitting position is recommended for blood pressure measurement. Height and body weight will also be recorded. On the day of imalumab administration, vital signs will be taken within 30 minutes prior to dosing and within 30 minutes after completion of imalumab infusion. Weekly monitoring to be done in Cycle 1 only, then Q2W.

Continued on next page

Continued

- ^f The 12-lead ECG assessment at Screening should be performed no earlier than 1 week before C1D1. The 12-lead ECG assessment should be performed predose and 2 (\pm 1) hours postdose on Day 1 (Baseline, C1D1).
- ^g Laboratory assessments should be evaluated before drug administration. Immediately prior to Cycle 1, laboratory assessments can be performed either on Day -1 or on Day 1 predose. Hematology tests will be done weekly during each treatment cycle. Chemistry/coagulation tests will be done on Day 1 and Day 15 of each treatment cycle, and Day 8 of Cycle 1 only. Laboratory tests include hematology (complete blood count with differential and platelet counts) and biochemistry (creatinine, creatinine clearance according to Cockcroft-Gault, sodium, potassium, calcium, magnesium, glucose, albumin, alanine aminotransferase, aspartate aminotransferase, alkaline phosphatase, total bilirubin, C-reactive protein, and blood urea nitrogen). Coagulation panel includes International Normalized Ratio and activated partial thromboplastin time.
- ^h Serum human chorionic gonadotropin to be tested at screening; urine dipstick test to be performed on Day 1 of each cycle (prior to dosing), End of Study/Early Termination Visit, and at Safety Follow-up. A serum pregnancy test will be performed to confirm if a positive result is obtained in a dipstick test.
- ⁱ If not readily available, genetic testing for KRAS/NRAS mutation status needs to be done early enough to allow randomization within 4 weeks. If KRAS mutation status is known, the subject can start treatment while NRAS testing is pending.
- ^j Baseline CT or MRI scans can be accepted within 28 days prior to first imalumab administration (C1D1); assessments are to be repeated every 2 cycles using the same method at each measurement and tumor response evaluated before starting the next cycle. A 7-day window is permitted for all imaging studies for tumor measurement purposes.

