Table 4 Schedule of Study Procedures and Assessments: SoC Following Randomization (4-Week Cycles or if Subject is on Best Supportive Care)								
Trial Periods	Screening Visit	Baseline Visit	Study Visits Per Treatment Cycle ^a				End of Study/ Early Termination Visit	Safety Follow-Up Visit ^b
Study Days	Days -28 to -1	Day 1 Predose	Days 1 to 7	Days 8 to 14	Days 15 to 21	Days 22 to 28		
Treatment Schedule								
EORTC QLQ-C30		X					X	X
EORTC QLQ-CR29		X					X	X
EQ-5D		X					X	X
12-lead ECG ^f	X	X	Day 1				X	X
ECHO/MUGA	X							
Hematology ^g	X	X	Day 1	Day 8	Day 15	Day 22	X	X
Chemistry/coagulation ^g	X	X	Day 1	Day 8 (Cycle 1 only)	Day 15		X	X
Pregnancy test ^h (if applicable)	X	X	Day 1				X	X
Urinalysis	X	X	Day 1				X	X
Genetic testing ⁱ (KRAS/NRAS)	X							
Tumor measurement (RECIST v1.1) ^j	X					Day 28 of Cycle 2 and then every other cycle	X ^k	X ^k
Adverse Event ^l	X	X	X	X	X	X	X	X

Table 4 Schedule of Study Procedures and Assessments: SoC Following Randomization (4-Week Cycles or if Subject is on Best Supportive Care)									
Trial Periods		Screening Visit	Baseline Visit	Study Visits Per Treatment Cycle^a				End of Study/ Early Termination Visit	Safety Follow-Up Visit^b
Study Days	Procedures/Assessments	Days -28 to -1	Day 1 Predose	Days 1 to 7	Days 8 to 14	Days 15 to 21	Days 22 to 28		
Treatment Schedule									
Concomitant medications/non-drug therapies		X	X	X	X	X	X	X	X

Abbreviations: AE=adverse events; C1D1=Cycle 1 Day 1; cfDNA=cell-free DNA; CT=computerized tomography; ECG=electrocardiogram; ECHO=echocardiogram; ECOG PS=Eastern Cooperative Oncology Group Performance Status; EORTC QLQ-C30=European Organization for Research and Treatment of Cancer Quality of Life Questionnaire Core 30; EORTC QLQ-CR29=European Organization for Research and Treatment of Cancer Quality of Life Questionnaire for colorectal cancer 29; EQ-5D=European Quality of Life – 5 Dimensions; IRT=Interactive Response Technology; MRI=magnetic resonance imaging; MUGA=multigated acquisition scan; Q2W=every 2 weeks; RECIST=Response Evaluation Criteria in Solid Tumors; SoC=standard of care.

^a Treatment cycles for SoC are defined in this study as 3-week or 4-week cycles. Treatment cycles will continue until progression, unacceptable toxicities, or withdrawal of consent.

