This will be regardless of whether the subject receives another anti-cancer therapy prior to progression. Subjects who have not progressed or died at the time of analysis will be censored at the time of the latest date of assessment from their last evaluable RECIST assessment. However, if the subject progresses or dies after two or more missed tumor assessments, the subject will be censored at the time of the latest evaluable RECIST assessment. If the subject has no evaluable visits or does not have baseline data they will be censored at 1 day unless they die within two visits of baseline. For this study, the exact time period that identifies that two tumor assessments have been missed will be defined as twice the protocol-defined time between scans + the protocol allowed visit window. RECIST assessments are scheduled to occur every other cycle, ie, every 8 weeks \pm 1 week. If tumor scans indicate progression or the subject dies more than $2*9$ weeks=18 weeks (126 days) after the previous tumor assessment, the subject will be censored on the date of the assessment prior to progression or death.

Table 2 below specifies the date of disease progression or censoring rules that will be carried out for the PFS analysis:

Table 2: Date of Progression or Censoring for Progression-free Survival

Situation	Date of Disease Progression or Censoring	Outcome
Alive with no post-baseline assessments for tumor response	Treatment start date	Censored
Disease progression or death after two or more consecutive missed tumor response assessments	Date of last scan for tumor assessment showing no evidence of disease progression that is before the first missed visit.	Censored
Not known to have progressed or died according to data in the database as of data-cut-off	Date of last scan for tumor assessment showing no evidence of disease progression	Censored
Withdrawal from the study or loss to follow-up	Date of last scan for tumor assessment prior to withdrawal or loss to follow-up	Censored
Disease progression reported on multiple response assessments	Earliest Date of Progression as defined in this Section	Progressed
Death without Disease Progression	Date of death	Progressed

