- ^f The 12-lead ECG assessment at Screening should be performed no earlier than 1 week before C1D1. The 12-lead ECG assessment should be performed predose and 2 (\pm 1) hours postdose on Day 1 (Baseline, C1D1).
- ^g Laboratory assessments should be evaluated before drug administration. Immediately prior to Cycle 1, laboratory assessments can be performed either on Day -1 or on Day 1 predose. Hematology tests will be done weekly during each treatment cycle. Chemistry/coagulation tests will be done on Day 1 and Day 15 of each treatment cycle, and Day 8 of Cycle 1 only. Laboratory tests include hematology (complete blood count with differential and platelet counts) and biochemistry (creatinine, creatinine clearance according to Cockcroft-Gault, sodium, potassium, calcium, magnesium, glucose, albumin, alanine aminotransferase, aspartate aminotransferase, alkaline phosphatase, total bilirubin, C-reactive protein, and blood urea nitrogen). Coagulation panel includes International Normalized Ratio and activated partial thromboplastin time.
- ^h Serum human chorionic gonadotropin to be tested at screening; urine dipstick test to be performed on Day 1 of each cycle (prior to dosing), End of Study/Early Termination Visit, and at Safety Follow-up. A serum pregnancy test will be performed to confirm if a positive result is obtained in a dipstick test.
- ⁱ If not readily available, genetic testing for KRAS/NRAS mutation status needs to be done early enough to allow randomization within 4 weeks. If KRAS mutation status is known, the subject can start treatment while NRAS testing is pending.

Continued on next page

Continued

- ^j Baseline CT or MRI scans can be accepted within 28 days prior to first imalumab administration (C1D1); assessments are to be repeated every 2 cycles using the same method at each measurement and tumor response evaluated before starting the next cycle. A 7-day window is permitted for all imaging studies for tumor measurement purposes.
- ^k A tumor measurement should be obtained at the End of Study/Early Termination visit, if no disease progression was confirmed previously and this visit occurs > 4 weeks after the last scan; no additional scans will be required if disease progression is confirmed at this visit. A tumor measurement should be obtained at the Safety Follow-up visit, if no disease progression was confirmed previously and this visit occurs > 4 weeks after the last scan.

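### Only SAP 7.2.1.2 fixes scans to the calendar from randomisation; the protocol and the SAP's PFS section tie most scans to treatment cycles, so unequal cycle delays could shift progression dates (two minor SAP wording errors sit alongside)

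*SAP*

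**What the plan says.** SAP 7.2.1.2, which defines the response rate, requires radiology every 8 weeks with 7 days either way, "starting from date of randomization without delays for toxicity until protocol-defined disease progression is noted". No other passage in either document starts the scan clock at randomisation or rules out delay.

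Elsewhere most scans follow the treatment cycle:

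- Protocol 10.3.3.7: "scans will be conducted from Cycle 2 (Day 28) and then be repeated every other cycle".
- Protocol 11.2: "Day 28 of every second treatment cycle (ie, every 8 weeks".
- Protocol 20.2, Table 3 (imalumab) and Table 4 (4-week SoC or best supportive care): "Day 28 of Cycle 2 and then every other cycle".
- SAP 7.1.1, which derives PFS: "RECIST assessments are scheduled to occur every other cycle, ie, every 8 weeks", with a 1-week tolerance.
- SAP Appendix 16.1, in footnote j, says: "Baseline CT or MRI scans can be accepted within 28 days prior to first imalumab administration (C1D1); assessments are to be repeated every 2 cycles". This appendix reproduces only the imalumab schedule.

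One control group has no cycle anchor. Protocol 10.3.3.7 says: "Tumor measurements by CT or MRI scans will be conducted every 8 weeks in subjects receiving SoC in 3-weekly treatment cycles". Table 3 footnote j adds: "A 7-day window is permitted for all imaging studies for tumor measurement purposes".

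Two further statements in the SAP are wrong. Section 7.1.1 counts the 28-day limit for the baseline scan back from screening, whereas Protocol 11.2, Tables 3 to 5 and SAP footnote j count it from C1D1. Section 4.1 defines the missed-scan period as twice 8 weeks plus 1 week and prints the result as 18 weeks. Section 7.1.1 repeats that definition in words but then computes 2*9 = 18 weeks (126 days).

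**The concern.** Deaths are dated exactly, but progression is dated at the scan that shows it. If the scan moves with the cycle, a delayed cycle dates progression later with no change in the disease. When both arms slip alike, the comparison is little affected. When one arm slips more, or one arm contains subjects scanned by calendar, the log-rank test picks up a difference in scan timing. The trial is open-label, progression is read by the investigator, and the three PFS sensitivity analyses in SAP 7.3 (new therapy, missed scans, adding Part 1) do not address scan timing.

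The safeguard exists, but it sits in the response-rate section of the SAP. It is absent from the protocol that sites work from and from the SAP section that derives the primary endpoint.

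The baseline and missed-scan wording is not arm-specific. It matters because a programmer could follow it literally.

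**Working it through.** **Where the schedules agree.** Two 28-day cycles are 56 days, or 8 weeks, so the cycle rule reproduces the SAP interval when cycles start on time. Randomisation is listed at the C1D1 predose visit (Protocol 10.3.2), so the two starting points nearly coincide. For 3-week SoC, two cycles are 6 weeks, so the every-other-cycle wording of SAP 7.1.1 cannot apply to that group.

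**Where they part.** After k one-week slips, a cycle-tied scan falls 7k days after the calendar date. One slip (7 days) stays inside the window; two (14 days) do not, and the shift carries forward.

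**Design inputs (SAP 2.3).** Medians 2.4 and 4.25 months, hazard ratio 0.565, one-sided α 0.15, power 80%, allocation 2:1. Schoenfeld events = (1.036 + 0.842)² / [(2/9) × (ln 0.565)²] = 3.527 / 0.0724 = 48.7, against 48 in the plan. This reproduces.

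**Effect on the test.** Simulation under no treatment effect:

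- From the plan: 44:22 subjects, median 2.4 months in both arms, 12-month accrual, 20% drop-out at 6 months, cut at the 48th event, scans every 56 days ±7, unstratified log-rank test at 0.15.
- Assumed: exponential PFS; 15% of events are deaths; each 4-week cycle slips 7 days with probability p; calendar controls do not slip; a share q of progressors is caught by an End of Study or Safety Follow-up scan (Protocol 10.3.3.8, 10.3.3.9).

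Rejection rate, %, for p = 5 / 10 / 25%:

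| Scenario | q = 0 | q = 0.5 |
|---|---|---|
| No slip | 16.5 | 15.9 |
| All controls on the cycle rule, equal slip | 16.2 / 16.5 / 15.9 | 15.5 / 15.9 / 15.8 |
| Half of controls on the calendar | 17.4 / 18.3 / 20.9 | 17.3 / 17.4 / 17.5 |
| All controls on the calendar | 19.5 / 20.9 / 26.2 | 17.2 / 18.2 / 20.2 |
| Only controls slip (p = 25% only) | 8.8 | 12.5 |

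The last row comes from 2,000 trials (standard error up to 1 point); the others use 8,000 (0.4 to 0.5 points). All should be read as rounded, since they move by a few points with coding detail. The reference level is about 16%, not 15%. In the most adverse cell the average hazard ratio under no effect is 0.87 (0.93 with q = 0.5), against 0.98 with no slip. With the calendar rule in both arms (p = 25%, q = 0.5) rejection is 16.3%.

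The 26% is the largest value for slip rates up to 25%, not a mathematical limit. In a harsher run where every scan interval in one arm lengthens by 1 to 2 weeks, rejection is 29 to 35% if that arm is A and 5 to 8% if it is control. In the latter case power falls from about 80% to 65 to 71%.

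**Interval-censored test.** On the same data an exponential interval-censored test rejects in 15.5% of trials in the most adverse cell and in 15.3 to 16.9% over all scenarios run. The exponential form is true by construction here, so this supports the approach and not a particular implementation.

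**Baseline scan.** Screening may begin on Day -28. A limit of 28 days before screening therefore admits a scan up to 28 + 28 = 56 days before C1D1, against 28 days elsewhere.

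**Missed-scan period.** 2 × 8 + 1 = 17 weeks (119 days). 2 × (8 + 1) = 18 weeks (126 days), the figure the SAP uses. Only events on days 120 to 126 after the last scan depend on which reading is programmed.

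**The case against.** The strongest reply is that the documents contain one interval, not two. The protocol and SAP 7.1.1 equate two cycles with 8 weeks, and Protocol 10.3.3 says a new cycle should start after each 28 days. Protocol 10.3.3.1 allows drugs to be interrupted or stopped, which is not the same as postponing a cycle, and lets imalumab continue while its partner drug is held. All of this stands: the harm needs cycles to slip, and greater slip in Arm A is an assumption.

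Four stronger readings are tempting and are not supported.

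- *PFS is biased towards imalumab, with a true error of 26%.* That figure needs 25% slip in Arm A, every control on the calendar and no off-schedule scans. Table 4 exists for controls on the cycle rule, the protocol prescribes off-schedule scans, and slip confined to controls pushes the other way.
- *The SAP leaves delays for reasons other than toxicity open.* In SAP 7.2.1.2 a fixed origin, interval and window already cover any cause. The gap is that the other passages do not carry the rule.
- *SAP Appendix 16.1 sets a cycle rule for controls.* It covers imalumab only; the rule for 4-week SoC and best supportive care is in Protocol Table 4.
- *The SAP has two missed-scan thresholds.* Every printed result is 18 weeks, including the FAS definition in Protocol 13.2.

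It is also fair to say that new wording may come late. SAP 5.5 describes the interval from 33 to 48 events in the past tense, and version 1.0 is dated 2016 OCT 06. That weakens the wording change for scans already taken, but not the case for summarising scan times and adding a sensitivity analysis. For the baseline scan, SAP 5.3 already selects the scan closest before randomisation when there are several, and the protocol governs when scans are taken.

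**Conclusion.** The point holds as a missing rule in the operative protocol and in the SAP's PFS derivation, not as two conflicting intervals. Its effect depends on unequal cycle slippage, about which the documents say nothing. For assumed one-week slips in up to 25% of cycles, the nominal 15% error lies between just under 10% and about 26%. It is about 16% when the arms slip alike, and most intermediate cases fall between 17 and 21%. Those figures also rest on the assumed death share, calendar-control share and off-schedule scan share. Direction and size are therefore unknown, and the effect may be nil. Reconciling the passages is still worthwhile, because it protects the primary endpoint at little cost.

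The baseline-scan anchor and the missed-scan expression are plain errors of minor weight. Neither changes the governing figure of 28 days before C1D1 or of 18 weeks.

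**What to change.** (a) Reconcile the scan passages. In Protocol 10.3.3.7, 11.2 and Tables 3 to 5, SAP 7.1.1 and SAP Appendix 16.1, state the SAP 7.2.1.2 rule: every 8 weeks, ±7 days, from randomisation, in all arms and irrespective of cycle delays. Because many scans may already have been taken, also summarise days from randomisation to each scan by arm. Add to SAP 7.3 one interval-censored PFS sensitivity analysis, with progression placed between the last negative scan and the detecting scan and deaths dated exactly. Specify it unconditionally: making it depend on whether scan timing differs would need a threshold and would let the data choose the analysis.

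(b) In SAP 7.1.1, count the 28 days for the baseline scan back from C1D1, to match Protocol 11.2 and SAP footnote j.

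(c) In SAP 4.1 and 7.1.1, replace the verbal definition and the expression 2*8+1 with 2 × (8 + 1) = 18 weeks (126 days).

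Cost: no added planned scans, although some will fall off dosing-visit days. The protocol wording needs an amendment with the review described in Protocol 16.2. The SAP part is wording, one summary by arm (SAP 7.1.2 already plans by-subject scan listings) and one analysis of existing data.

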10.3.3.8 End of Study/Early Termination Visit

Subjects who experience disease progression or who discontinue early from the study will be asked to undergo an End of Study/Early Termination visit. All questionnaires will be completed prior to the start of any assessments.

The following assessments will be performed at this visit:

- EORTC QLQ-C30
- EORTC QLQ-CR29
- EQ-5D
- Vital signs (body temperature, heart rate, blood pressure, respiratory rate, and weight)
- Physical examination
- ECOG PS
- 12-lead ECG
- Clinical laboratory assessments (hematology, serum chemistry, and coagulation)
- Urine dipstick test for women of childbearing potential
- Urinalysis
- CT or MRI scans for tumor measurement (as assessed by RECIST v1.1), if no disease progression was confirmed previously and this visit occurs > 4 weeks after the last scan; no additional scans will be required if disease progression is confirmed at this visit.

- For subjects treated with imalumab, blood sample for immunogenicity (ADA and NADA)
- For subjects treated with imalumab, blood sample for cfDNA (genetic biomarkers)
- For subjects treated with imalumab, urine sample for cfDNA (genetic biomarkers)
- Collection of AEs
- Review of concomitant medications/non-drug therapies
- Entry into IRT System

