7. EFFICACY EVALUATION

7.1 Analysis of Primary Efficacy Outcome Measure

7.1.1 Derivation of Primary Efficacy Outcome Measure

The revised RECIST guidelines ([Eisenhauer et al., 2009](#)) will be used to determine disease progression. Date of disease progression is the earliest date of the imaging method to determine disease progression.

For an individual subject, the imaging method used to measure tumor burden at baseline should be used for each future tumor assessment. Baseline tumor measurements and identification of target lesions may be based on imaging obtained within 28 days prior to screening. Scheduled tumor response assessments must be interpreted prior to the start of the next treatment cycle.

Date of Progression will be derived as follows:

1. For progression based on new lesion(s), the date of progression is the first scan date on which the new lesion is detected.
2. For progression based on target lesions, , the date of progression is the date of the initial scan of target lesions showing >20% increase in the sum of diameters of target lesions;
3. For progression based on non-target lesions, the date of progression is the date of the first scan that indicated unequivocal progressive disease of existing non-target lesions.

The date of progression will be the earliest date among dates described above.

For tumor response evaluation from assessments on which multiple scans are done on different dates and no evidence of progression is indicated, the latest date of all scans will be considered as the evaluation date showing no evidence of progression for that assessment. In cases where one or more lesions (target or non-target lesions identified at baseline) do not have an assessment at a given post-baseline evaluation, the assessment

for tumor response for that visit will be considered “not evaluable (NE)” unless disease progression is noted.

PFS is defined as the time between randomization and tumor progression (per RECIST v1.1 criteria) or death from any cause, with censoring of subjects who are lost to follow-up or withdraw consent.

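### Clinical benefit rate counts stable disease with no minimum time, and unscheduled scans before Study Day 49 can supply it

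*SAP*

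**What the plan says.** SAP 7.2.1.2 defines CBR as the proportion whose best response is complete response, partial response or "stable disease (SD) per RECIST based upon the best response as assessed by the investigator". Response is judged "based on the revised RECIST guidelines (Version 1.1) at each radiographic assessment". One class of scan is set aside: "Results based upon scans performed after start of new anti-cancer therapy will be excluded when calculating the best overall response". The section gives no earliest date for a scan that can establish SD. The denominator is the Full Analysis Set (FAS). A living subject enters the FAS on any single post-baseline assessment (SAP 4.1).

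Protocol 10.3.3.7 places the first on-treatment scan at Cycle 2 Day 28, and Table 3 allows a 7-day window. Two other scans can come sooner:

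- Protocol 10.3.3.8 calls for a scan at the End of Study/Early Termination visit "if no disease progression was confirmed previously and this visit occurs > 4 weeks after the last scan".
- Protocol 10.3.3.9 applies the same condition at the safety follow-up visit, 30 (±7) days after the last dose.

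The last scan may be the baseline scan. Protocol 11.2 allows that scan up to 28 days before Cycle 1 Day 1 (C1D1). SAP 7.1.1 has a different window: "identification of target lesions may be based on imaging obtained within 28 days prior to screening". Protocol 11.2 also has best overall response determined at the End of Study/Early Termination visit.

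**The concern.** SD carries information about benefit only if enough time has passed for progression to have been possible. One might assume that the 8-week scan schedule guarantees this, but the unscheduled scans break that assumption. A subject who stops after one or two doses, is scanned at the exit or follow-up visit and is read as unchanged has a best response of SD and counts as a clinical benefit.

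Because the rule takes the best response, a later scan showing progression does not undo the early SD. Scan timing also decides how the subject is treated. A living early stopper with no post-baseline scan is outside the FAS, while the same subject with one early scan is inside it and scored as a success.

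CBR is a named secondary efficacy measure, compared between arms by Fisher's exact test. The trial is open-label, response is read by the investigator, and the arms are small.

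**Working it through.** **Plan's own figures.** The documents give no assumed rate, power or target for CBR, so there is no CBR figure to reproduce. The check borrows the PFS medians from SAP 2.3, so their consistency was tested first. The hazard ratio is 2.4/4.25 = 0.565. Schoenfeld's formula for 2:1 allocation, one-sided α 0.15 and power 0.80 gives (1.036 + 0.842)² / [(2/9) × (ln 0.565)²] = 48.7 events, against 48 stated.

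**First scheduled scan.** Cycle 2 Day 28 is Study Day 28 + 28 = 56. With ±7 days the window is Day 49 to Day 63.

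**Route 1, early-termination scan.** The condition is more than 28 days since the last scan. Day -k is k days before Day 1, so the earliest qualifying day is 1 + 29 - k.

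| Baseline scan | Earliest day the scan is called for |
|---|---|
| Day -28 | Day 2 |
| Day -21 | Day 9 |
| Day -14 | Day 16 |
| Day -7 | Day 23 |
| Day -1 | Day 29 |

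All of these precede Day 49. Under the SAP's wider baseline window the condition can already be met on Day 1.

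**Route 2, safety follow-up scan.** After a single dose on Day 1 the visit falls on Day 24 to Day 38, nominally Day 31. At Day 31 the gap from a baseline scan on Day -k is 30 + k days, that is 31 to 58 days for k = 1 to 28. The condition is met for every one of these baseline dates. At Day 24 the gap is 23 + k, so it is met when k is 6 or more. This route does not depend on an old baseline scan.

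**How little an early scan says.** Assume exponential PFS with the SAP medians: S(d) = exp(-ln 2 × d / (median × 30.4375)).

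| Days from start | Control (2.4 months) | Experimental (4.25 months) |
|---|---|---|
| 2 | 98% | 99% |
| 28 | 77% | 86% |
| 56 | 59% | 74% |

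Among those progression-free at 2 days, the share who progress or die by 56 days is 1 - 0.588/0.981 = 40% (control) and 1 - 0.741/0.989 = 25% (experimental). From 28 days the shares are 1 - 0.588/0.767 = 23% and 1 - 0.741/0.861 = 14%.

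**Effect on CBR.** Taking all 44 and 22 randomised subjects as the FAS, one such subject adds 1/44 = 2.3 points in Arm A or 1/22 = 4.5 points in Arm B. Four would add 9.1 or 18.2 points. The number of such subjects is not given in the documents.

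**The case against.** - **The Day 2 case is a corner case.** It needs a baseline scan at or near Day -28, and the protocol's language for the exit scan is advisory. The subject must also be read as SD and must not have started new anti-cancer therapy. This stands, so the claim is that such a subject can be counted, not that every immediate stopper will be. Route 2 is the more ordinary path and lacks the baseline-date condition.
- **Scanning continues after a toxicity stop.** SAP 7.2.1.2 asks for 8-weekly scans until progression, with no delay for toxicity. Many early stoppers would then have a Week 8 scan and, if still stable, would count properly. This also stands: only early SD without later qualifying SD is an artefact. It does not cure the rule, because an early SD followed by progression at Week 8 still has SD as its best response.
- **Consequence is limited.** SAP section 5 treats secondary p-values as descriptive, the best-response categories are tabulated and scan results are listed by subject. As an illustration, start from equal rates of 26/44 and 13/22 and add four Arm A subjects: 30/44 against 13/22 gives a two-sided Fisher p of 0.59. This stands and limits the weight of the point.

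A reader might infer that early toxicity stops will make imalumab look more effective. The documents do not support this. They give one common drop-out rate (20% at 6 months) and no early-stop rate by arm. Arm B is investigator's choice, and Protocol 6.1.5.4 describes one approved agent, regorafenib, as severely toxic in most subjects. The distortion could run either way.

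**Conclusion.** The point holds as a gap in the CBR rule. SD has no minimum time, and the scan schedule does not impose one, because exit and safety follow-up scans can precede Day 49. An uninformative early SD can be counted as clinical benefit and survives later progression.

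The size that can be stated is 2.3 points per affected subject in Arm A and 4.5 in Arm B, assuming the FAS equals the 44 and 22 randomised. Any total, or any net difference between arms, would need early-stop rates that the documents do not contain. The survival percentages rest on exponential PFS at the planning medians and only illustrate how little an early scan shows.

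The objective response rate does not count SD, so the missing SD minimum does not bear on it. The primary PFS analysis and its sample size are unaffected.

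**What to change.** Add to SAP 7.2.1.2: SD counts as best response toward CBR only if documented on or after Study Day 49, with C1D1 as Day 1. Earlier SD with no later evaluable assessment is classed as not evaluable and stays in the FAS denominator. If the next assessment after an early SD shows progression, best response is progressive disease.

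Day 49 is the opening of the protocol's first scheduled scan window (56 - 7). State it as a study day: 49 days after a Day 1 randomisation is Study Day 50, which would reject a scan inside the protocol window. The documents supply no SD threshold, so this value is a choice taken from their own schedule.

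The baseline-scan windows in Protocol 11.2 and SAP 7.1.1 should be reconciled at the same time, although the Day 49 rule works under either.

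The cost is a few sentences in the SAP and no new data. The reported CBR may be slightly lower.
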